4.1 General Design

This cluster-randomized trial will be conducted with 14 Philadelphia CMHCs, 7 randomized to ATTOC and 7 to usual care (UC). Following randomization, study staff will visit sites to recruit clinic personnel and clients over a 4 to 6 week period. Those eligible will complete informed consent and HIPAA forms and a baseline assessment to establish pre-intervention levels on all measures (baseline). After 4-6 weeks, the ATTOC intervention will be implemented over 9 months, from Week 1 to Week 36 (with UC at the control sites). Two mid-intervention assessments (Weeks 12 and 24) will allow for performance feedback (see Outcomes Data) and mediational analyses. Week 36 (end-of-treatment; EOT) and 52 (3-months post-EOT) assessments will allow for evaluation of changes on outcomes between groups over time. All measures will be conducted at the respective CMHC

(or over the phone if necessary) and 7-day point prevalence smoking cessation will be verified using a breath carbon monoxide (CO) monitor (abstinence = < 8ppm; [93]). Figure 1 illustrates the study design.

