4.7 Study Measures

Screening

- **Community Mental Health Clinic Eligibility Screen:** The assessment will be completed by a CMHC leader such as a CEO and contains questions that will assess eligibility criteria as well as organizational readiness (the latter will be accomplished with the ORIC). The results of this assessment will be taken into account during clinic intervention randomization.
 - **Organizational Readiness for Implementing Change (ORIC):** This psychometric assessment measures change commitment and change efficacy [92] in prospective CMHCs. This assessment includes a scale with 12 questions.
- **Clinic Leadership Informed Consent Acknowledgement:** A designated clinic leader will review the informed consent and will complete the inform consent acknowledgement form. This form was devised to help ameliorate possible concerns regarding undue coercion surrounding clinic personnel recruitment. This form is included for review by the personnel participants during the informed consent process.
- **Client and Personnel Eligibility Screen:** These brief assessments contain questions based on inclusion and exclusion criteria to ensure study eligibility.

Covariates

- **Client Psychiatric History:** Among clients, we will collect self-reported data on past and current psychiatric conditions/diagnoses, duration of illness, and lifetime frequency of psychiatric hospitalizations. Psychiatric diagnosis will be confirmed via data requested from CBH.
- **COVID-19 Quitting Experience Questionnaire:** The purpose of this survey is intended to capture the participant's experience quitting smoking during the COVID-19 pandemic. The survey will be administered at baseline for personnel. The survey will include 24 questions recommended by the NIH for research pertaining to COVID-19, 11 questions related to smoking behavior and the pandemic formulated by staff, and the PHQ-2 and GAD-2 measures for depression and anxiety symptoms (4 questions total).

Mediators:

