At the conclusion of the Environmental Scan, an overall client, staff, environment, and agency ratings are given. The ATTOC Consultant team rejoins the Leadership Team to discuss the agency’s observed preparedness to address tobacco and to begin to formulate the agency’s change plan to identify specific objectives for tobacco assessment, treatment, and policies.

- **ATTOC Communication Plan:** Step 5 of the ATTOC Approach addresses the importance of supporting the Change Plan by developing a Communication Plan to facilitate internal and external communication needs. It is a way to communicate with stakeholders, determine channels for feedback, and to communicate new policies and procedures. This tool is used to familiarize the personnel participants with current clinic communication processes and resources and provides a framework for designing a new plan of action in this area.

Outcomes Data:

- **Client Prescription Data:** Client participant prescription data (for cessation medications or NRTs) will be requested from CBH.
- **Time Line Follow-Back (TLFB):** This assessment utilizes a structured interview method to assess smoking rates. Using a calendar with sufficient days from the prior assessment time point, study staff work with the participant to formulate a clear picture of whether abstinence was achieved each day. The purpose of the interview will be to reconstruct the participant's smoking practices, on a daily basis if possible. Beginning with current smoking habits, the staff member prompts the participant to recall previous smoking rates in a backward chronological fashion.
- **CO Form:** This assessment collects the CO reading (in parts per million) as well as smoking rate in the 24 hours preceding data collection and the time since the participant's last cigarette.
- **Revised Behavior and Symptom Identification Scale (BASIS-R):** Clients will complete the Revised Behavior and Symptom Identification Scale (BASIS-R), a 24-item assessment of mental health functioning [108] that yields a total score and subscale scores for: depression, interpersonal relationships, self-harm, emotional lability, psychosis, and substance abuse.
- **Client Hospitalization Assessment:** We will assess the frequency and duration of any illness-related in- client hospitalization. This self-report measure will be confirmed via data requested from CBH.

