4.8 Study Endpoints

4.8.1 Primary Study Endpoints

For Aim 1, we will assess adherence to guidelines for treating TUD as done previously [18, 31, 72, 73]. This measure, developed by Delucchi et al. [103], assesses components of the USPHS guideline [20]. Items measure the rate of: asking clients about smoking, advising them to quit, providing assistance with quitting, and arranging visits to track progress. A total adherence score can be calculated [18]. We will supplement this measure with questions about the content, nature, and intensity (in terms of time) of behavioral counseling provided. Clinician adherence will be assessed from the client perspective as well, using the client version of this scale [105], EHR adherence data will be accessed (e.g., documenting smoking status, use of pharmacotherapy), and prescription data (provided and filled) will be accessed by CBH.

For Aim 2, smoking status is assessed using self-reported 7-day point prevalence and CO to verify self-report [66, 106], with abstinence=self-reported abstinence for >7 days prior to the weeks 36 and 52 assessment and a breath CO <8ppm at the time-point [98, 99]. Participants are assumed to be smoking if they self-report to be smoking at the time-point, do not provide self-report or CO data at the time-point, or provide a breath sample at the time-point that is >8ppm [93]. Secondary outcomes will also be assessed (e.g., smoking status at week 12, smoking rate [number of cigarettes/day]).

For Aim 3, client mental health will be measured using several indicators [107]. We will assess the frequency and duration of any illness-related in- client hospitalization (available through the EHR). Clients will complete the Revised Behavior and Symptom Identification Scale (BASIS-R), a 24-item assessment of mental health functioning [108] that yields a total score and subscale scores for: depression, interpersonal relationships, self-harm, emotional lability, psychosis, and substance abuse. The Short-Form Health Survey (SF-12) will assess physical and mental QOL [109, 110].

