Client/Personnel Eligibility Screen		X											
TREATMENT													
ATTOC			X	X	X	X	X	X	X	X	X	X	
UC			X ²										
MEASURES													
COVARIATES													
Demographics, Smoking History & FTND (S-KAP, S-KAS)		X				X			X			X	X
Client Psychiatric History ²		X											
Client COVID-19 Questionnaire		X											
Clinic/Clinician Change (The Dashboard)			X	X	X	X	X	X	X	X	X	X	
MEDIATORS													
Personnel Knowledge and Attitudes (S-KAP)		X				X			X			X	X
Client Knowledge and Attitudes (S-KAS)		X				X			X			X	X
TREATMENT DATA													
ATTOC Intervention Adherence (The Dashboard)			X	X	X	X	X	X	X	X	X	X	
ATTOC Change Plan			X			X							
ATTOC Environmental Scan			X			X							
ATTOC Communication Plan			X			X							
OUTCOMES													
Adherence to TUD Guidelines (S-KAP)		X				X			X			X	X
Adherence to TUD Guidelines (S-KAS)		X				X			X			X	X
Adherence to TUD Guidelines (Client Prescription Data) ²												X	X
Client Smoking Status (CO Form)		X											
Client Smoking Status (TLFB)						X			X			X	X
Client Mental Health (BASIS-R)		X				X			X			X	X
Client QOL (SF-12)		X				X			X			X	X
Client Hospitalization Form ²												X	X
Treatment and Client Costs		X										X	X

¹ Activities associated with this timepoint may occur any time within the 4-6 week period directly preceding Week 1.

² Data provided by request from Community Behavioral Health (CBH)

³ This is a one-day training lead by [name] and/or [name].

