6.1.1 Baseline

Eligible and interested client and clinic personnel participants will complete informed consent and HIPAA documents and baseline assessments. Following receipt of informed consent and HIPAA authorization, a baseline assessment will be completed. The baseline assessments will collect a broad range of data, including demographics and smoking history for both participant groups and psychiatric history data for client participants. Client participants will also complete a smoking status review (CO Form), the BASIS-R, SF-12 and a hospitalization assessment. Additionally, personnel participants will complete the Smoking Knowledge, Attitudes, and Practices (S-KAP) survey and client participants will complete the Smoking Knowledge, Attitudes, and Services (S-KAS) survey. [105]. At UC clinics, baseline assessments help ensure that any differences across UC sites at baseline can be controlled for in subsequent analyses. Compensation for the baseline session will be distributed when baseline questionnaires have been completed. For those participants (either personnel or clients) who complete the informed consent and HIPAA documents, but cannot complete the baseline assessments until a later date, payment will be deferred until baseline questionnaires have been completed. An appointment will be made with the participant to ensure that all session questionnaires are completed and compensation provided.

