7.2.1 Analysis of Outcomes of Interest

The effects of the ATTOC model on provider adherence to guidelines for treating TUD: We hypothesize that the ATTOC intervention will increase adherence to guidelines for treating TUD vs. UC. The outcome is continuous and the hypothesis will be tested by a treatment arm term in a mixed-models linear regression model that may include covariates. Mixed models may account for individual level clustering inherent in longitudinal studies and site level clustering. Outcomes of the analysis will be characterized by regression coefficients and confidence intervals. Significance will be determined from a z-score corresponding to the treatment variable. Although level of adherence at 36 and 52 weeks will represent our primary outcome variables, similar regression analyses will be performed for assessments at Weeks 12 and 24. Also, we can examine models of specific clinician practices (e.g., identifying smoking, recommending pharmacotherapy) and examine adherence from the client perspective and based on adherence data ascertained from the EHR.

The effects of the ATTOC model on client smoking: The hypothesized effect of treatment arm (i.e., the difference in quit rates between subjects receiving the ATTOC intervention or UC) will be tested by a treatment arm term in a mixed-models logistic regression model with covariates. Outcomes of the analyses will be characterized by odds ratios (e.g., odds of quitting smoking) and 95% confidence intervals. Although quit-rates at the end of 36 and 52 weeks will represent our primary outcomes, similar analyses will be performed for other assessments of quit rates (e.g., at Weeks 12 and 24). In addition, as many participants will fail to become abstinent, we will explore the use of zero-truncated negative binomial regression for count data to examine the main effects of treatment arm on changes in smoking rate at all assessment time-points.

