The effects of the ATTOC model on client mental health functioning and QOL: We will compare treatment arms in terms of the frequency of hospitalizations (binary) and mental functioning evaluations (continuous) over 52 weeks. Again, we will use mixed models to account for clustering, while accommodating either the binary outcome with logistic regression or the continuous measures with linear regression. Equivalence uses two one-sided tests against lower and upper equivalence bounds. The null hypothesis is that the groups are not equivalent and are determined to be equivalent when the mean or proportion is significantly different from both boundaries. We will use this approach to determine whether hospitalization rates are higher (null) in the ATTOC group or equivalent, and whether mental functioning is lower in the ATTOC group (the null) or equivalent. All hypotheses will be tested at $\alpha=0.05$ (0.025 for any one sided non-inferiority test).

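### The Aim 3 hospitalisation endpoint runs over 52 weeks, but no matching pre-intervention window is defined, the sections disagree on whether it is assessed at baseline, and no adjustment for prior admission is pre-specified

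*Combined protocol and SAP*

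**What the plan says.** - **Endpoint.** Section 4.8.1 (Primary Study Endpoints, Aim 3): "We will assess the frequency and duration of any illness-related in- client hospitalization (available through the EHR"). Section 7.2.1: "We will compare treatment arms in terms of the frequency of hospitalizations (binary) and mental functioning evaluations (continuous) over 52 weeks".
- **Baseline promise.** Section 4.1 describes "a baseline assessment to establish pre-intervention levels on all measures (baseline").
- **Baseline history.** Section 4.7, Client Psychiatric History: "we will collect self-reported data on past and current psychiatric conditions/diagnoses, duration of illness, and lifetime frequency of psychiatric hospitalizations". That paragraph mentions CBH confirmation for diagnosis only.
- **Baseline assessment, text.** Section 6.1.1: "Client participants will also complete a smoking status review (CO Form), the BASIS-R, SF-12 and a hospitalization assessment". No look-back period is given.
- **Baseline assessment, schedule.** In the section 6 table the row "Client Hospitalization Form" is marked at Weeks 36 and 52 and not at baseline. Section 6.2.5 also places it at Weeks 36 and 52.
- **Records.** Section 4.7 (Client Hospitalization Assessment), a footnote to the schedule table and section 9.2 all say that hospitalisation data are supplied or verified by CBH. None gives start or end dates for the request.
- **Adjustment.** Under section 7.2, variables related to arm or to follow-up completion at p < .10 may enter as covariates. Prior hospitalisation is not named.
- **Design.** Section 4.2 matches clinics on size and readiness, and recruits clients only after their clinic is randomised. Section 4.1 gives 7 clinics per arm.

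**The concern.** Aim 3 is a safety claim: that ATTOC does not worsen mental health. With recruitment after randomisation, the clients who enrol may differ in severity by arm, and with 7 clinics per arm chance differences can also be large. Admission in the year before the intervention, defined as the endpoint is, would be the most direct check on whether the arms began with the same admission risk. A lifetime count mixes age and length of illness with current risk. If the arms differ at the start, a difference at 52 weeks could look like harm without being harm, and a true harm could be hidden. Whether anyone adjusts for this is left to a p-value screen across few clusters.

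**Working it through.** **1. The plan's own power figure.** Section 7.1 gives 14 sites, 700 clients, 15% loss, a national non-hospitalisation rate of 88.6%, a floor 20% below it, and ICC up to 0.15. Section 7.2.1 gives one-sided 0.025.

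- Clients per clinic: m = 700 × 0.85 / 14 = 42.5, or 297.5 per arm.
- Design effect: 1 + 41.5 × 0.15 = 7.225. Effective n per arm: 297.5 / 7.225 = 41.2.
- SE = √(2 × 0.886 × 0.114 / 41.2) = 0.070.
- Power at a 20-point margin: Φ(0.20/0.070 − 1.96) = 81.5%.

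The stated 80% is reproduced with no baseline covariate. If the 20% is read as relative (0.2 × 88.6 = 17.7 points), power is 71.6%. The plan does not say which reading is meant.

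**2. Chance imbalance before the intervention.** Assume a prior-year rate equal to the national 11.4%, with 50 clients in each clinic. The between-arm SD is √[2 × 0.114 × 0.886 × (1 + 49 × ICC) / 350]:

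| ICC | SD of the arm difference (points) |
|---|---|
| 0 | 2.4 |
| .05 | 4.5 |
| .15 | 6.9 |

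This is the chance part only. Any selective enrolment after randomisation would add to it.

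**3. What adjustment could gain.** Take p = 0.10 (the plan's 90% non-hospitalisation) and m = 42.5. On the risk-difference scale,

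Var = (2/7) × [ICC × 0.09 × (1 − r_c²) + (1 − ICC) × 0.09 × (1 − r_w²) / 42.5],

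where r_c and r_w are the clinic-level and within-clinic correlations of prior-year admission with the outcome. The documents give neither, so the values below are assumptions.

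Example at ICC .15: unadjusted, (2/7) × (0.0135 + 0.0018) = 0.00437, SE 6.61 points. With 0.5/0.2, (2/7) × (0.0135 × 0.75 + 0.0018 × 0.96) = 0.00339, SE 5.82 points.

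| r_c / r_w (assumed) | SE, ICC .05 | SE, ICC .10 | SE, ICC .15 | Reduction |
|---|---|---|---|---|
| none | 4.31 | 5.58 | 6.61 | – |
| 0.3 / 0.1 | 4.17 | 5.37 | 6.34 | 3-4% |
| 0.5 / 0.2 | 3.89 | 4.95 | 5.82 | 10-12% |
| 0.7 / 0.3 | 3.43 | 4.25 | 4.93 | 20-25% |

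The comparator here is no adjustment at all. If the covariates already collected reached 0.5/0.2 and prior-year admission raised this to 0.6/0.25 (also assumed), the further reduction would be 5-7% at ICC .05-.15 and 3% at ICC .01.

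The formula is for a linear risk difference and uses both clinic-level and client-level information. Section 7.2.1 plans mixed logistic regression, so the percentages are a guide and do not transfer exactly.

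**The case against.** **Severity is measured at baseline.** BASIS-R, SF-12, diagnoses, illness duration and the lifetime count are all collected, and section 7.2 allows adjustment for variables related to arm. A reader might infer that severity at enrolment cannot be separated from harm. The documents do not support that: partial control is available. What stands is that none of these measures is on the endpoint's own scale and none is pre-specified for this model.

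**The history is not purely self-report.** Section 9.2 says hospitalisation information is verified through CBH, and the Psychiatric History row of the schedule carries the CBH footnote. The request may therefore already reach back before enrolment. Its dates are not given, so neither its adequacy nor its absence can be asserted. The hospitalisation form itself is not in the documents, so its look-back cannot be judged either.

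**The precision gain is uncertain.** A reader might conclude that the comparison is needlessly imprecise. That is not shown. The gain rests on assumed correlations, is small if these are weak, and shrinks further against covariates already planned.

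**Smoking rate.** A reader might see the same gap in cigarettes/day. Section 7.2.1 explores "changes in smoking rate at all assessment time-points", yet the Time Line Follow-Back is not marked at baseline. However, that interview is built "Using a calendar with sufficient days from the prior assessment time point", so a baseline version does not follow from its definition. The schedule marks smoking history at baseline and at Weeks 12, 24, 36 and 52. If that item records cigarettes/day, a common scale already exists and no baseline Time Line Follow-Back is needed.

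**Conclusion.** The point holds in a limited form. A primary safety endpoint over 52 weeks has no defined pre-intervention counterpart over a matching period, the plan contradicts itself on whether hospitalisation is assessed at baseline, and adjustment for prior admission is left to an optional screen. The main stake is interpretation. A chance difference between arms with an SD of 4.5 to 6.9 points at ICC .05-.15 is large beside an outcome of about 10%, and the measures collected would account for only part of it. That range assumes a prior-year rate of 11.4% and 50 clients per clinic.

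Precision is a secondary benefit: an SE reduction of roughly 3% to 25% against no adjustment at ICC .05-.15, on assumed correlations, and less in practice. The comparison is not invalid without the change, and the stated power stands or falls independently of it.

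**What to change.** 1. Reconcile section 6.1.1 with the schedule table and section 6.2.5 on whether hospitalisation is assessed at baseline.
2. Define the CBH request to cover admissions in the 52 weeks before each clinic's Week 1, for all enrolled clients in both arms, with the same definition of admission as the endpoint. Mark it in the baseline column.
3. Give the section 6.1.1 assessment the same 52-week window.
4. Tabulate prior-year admission by arm.
5. In section 7.2.1, pre-specify client-level prior-year admission (yes/no) as a covariate in the hospitalisation model, whatever the result of the p < .10 screen.
6. For change in smoking rate, name the repeated smoking-history item as the common scale, if it records cigarettes/day.

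**Cost:** a longer look-back in a data request already planned, one mark in the table, a few lines of analysis text and one model term. If the CBH records reach back far enough, clients already enrolled can be covered without new contact. Clients without CBH coverage for part of the prior year would have incomplete history, so the plan should say how they are handled.

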
Statistical Methodology
	
 • Sample characteristics will be assessed by treatment arm and site with chi-square or regression for their relationship to completion of outcomes (variables related to treatment arm or completion of follow-ups may be covariates in analyses.) • Fidelity and adherence measures will be evaluated across treatment arms, and the measures can be included in primary analyses. • Rate of missing data will be assessed as related to a range of variables using chi-square and regression and using appropriate methods for dealing with missing data.

Data and Safety Monitoring Plan
	
The study will be monitored by the PIs and co-investigators, and regulatory committees at the University of Pennsylvania (i.e., IRBs, OHR) as well as by a study specific Community Advisory Council and the Philadelphia Department of Public Health Institutional Review Board. During the course of the study, safety and data quality monitoring will be performed on an ongoing basis by the Principal Investigators and the study staff.

2 Introduction

The information that follows constitutes the research protocol for the Testing an Organizational Change Model to Address Smoking in Mental Healthcare study. This study will be conducted in compliance with the provisions set forth in this document. This study will also be conducted in full accordance with all applicable University of Pennsylvania Research Policies and Procedures, Good Clinical Practice Standards and all applicable Federal and state laws and regulations including 45 CFR 46, 21 CFR Parts 50, 54, 56. All episodes of noncompliance will be documented.

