- **ATTOC Intervention Adherence Tool (“The Dashboard”):** This web-based tool is used by the study team to track and monitor compliance and progress on the 10 ATTOC steps – on an organizational and on an individual (clinician) level. This adherence measure is used to determine the level of compliance with ATTOC steps so that variability across sites in the implementation of ATTOC can be included in analyses and to guide performance feedback. The dashboard is a visual figure with a numeric indicator using red (no movement), yellow (some progress), and green (completed) colors that enables staff to see progress on key metrics of change. Data are gathered through staff self-report and chart reviews, study measures, and the environmental scan. On an organizational level, examples of metrics include: the selection of a site champion, the use of change and communication plans, the implementation of change plans, additional staff training, the provision of TUD treatment (counseling, referrals, pharmacotherapy), the establishment of a smoke-free campus or progress in establishing smoking restrictions, use of no-smoking signage, inclusion of TUD treatment within SOPs, and provision of TUD treatment brochures. On an individual level, examples of metrics include: the provision of TUD counseling, number of referrals to smoking cessation treatment programs including the Quit-line, and the provision of pharmacotherapy. This dashboard assessment reflects metrics of overall organizational and individual clinician change and is used as a covariate in analyses of study aims and to guide performance feedback to clinic leadership, site champions, and clinicians. We will also include a measure of fidelity to determine whether the ATTOC model was implemented as intended. This measure includes: attendance at on-site training sessions, logging onto the ATTOC program training website, and participation in training teleconference/video calls. The fidelity measure, analogous to a measure of treatment dose, will be expressed as a proportion of the number of training hours received and used as a potential covariate. All personnel participants are expected to interact with the Dashboard and update the metrics. The chosen site champion will be responsible for reviewing the metrics prior to scheduled training sessions and will summarize the findings for the group.

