- Meet with agency Executive Director/CEO to review ATTOC phases and steps, establish a shared vision, enlist support, and establish the commitment to climate and culture change (step 1);
- Meet with Tobacco Champion/Leadership Group to establish a collaborative and shared plan for training and culture change that is consistent with ATTOC and the needs of the individual agency (step 2);
- Perform an Environmental Scan (step 3), which includes meeting with agency leaders, staff, and clients for a baseline organizational assessment, providing realistic targets for change across 3 domains: 1) the client-level assessment evaluates client flow, clinical charts, and use of current tobacco treatment, 2) the staff-level assessment evaluates staff smoking and treatments available to staff, level of prior training on TUD, and staff attitudes/beliefs towards this initiative and TUD treatment; and 3) the environmental assessment evaluates the indoor and outdoor spaces of the agency for evidence of tobacco use, available literature to support TUD recovery, and agency policies. The Environmental Scan includes a walk-around the facility, interviews with staff and clients, and chart reviews to assess documentation of tobacco use and treatment. This evaluation creates a baseline assessment of the core goal areas for the ATTOC intervention, helps assess organizational readiness, and provides important information for the Change Plan (step 4). A central feature of ATTOC is the “dashboard”, a formal comprehensive measure with indices of each aspect of the Environmental Scan, such as existing policy and adherence to TUD clinical guidelines. Subsequent dashboard assessments are used by the agency Champion/Leadership and ATTOC consultants to gauge progress and guide performance feedback.
- Written Change Plans and time-lines are provided based on the Environmental Scan and the initial dashboard assessment, material required for change is prepared, and a written communication plan is provided which guides efforts to promote culture change (steps 4 and 5);

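### The Dashboard, a post-randomisation measure of ATTOC implementation, may enter the primary arm comparisons for Aims 1 to 3 as a covariate

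*Combined protocol and SAP*

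**What the plan says.** - **Section 4.7, Treatment Data.** The Dashboard reflects overall organisational and "individual clinician change and is used as a covariate in analyses of study aims". No aim is excepted. An earlier sentence gives a dose-type purpose: compliance is measured "so that variability across sites in the implementation of ATTOC can be included in analyses". The separate fidelity measure, a proportion of training hours received, is to be "used as a potential covariate".
- **Study Summary and Section 7.2, in the same words.** "Fidelity and adherence measures will be evaluated across treatment arms, and the measures can be included in primary analyses".
- **Section 7.2.1.** Aims 1 and 2 are tested by a treatment-arm term in a mixed model. Covariates are optional for Aim 1 and included for Aim 2, and neither list is given. Aim 3 uses mixed models and says nothing about covariates.
- **Schedule in Section 6.** The row "Clinic/Clinician Change (The Dashboard" stands under covariates and "ATTOC Intervention Adherence (The Dashboard" under treatment data. Both are marked from Week 1 to Week 36, with no mark at Baseline.
- **Section 6.2.2.** The Dashboard is a formal measure "with indices of each aspect of the Environmental Scan, such as existing policy and adherence to TUD clinical guidelines". Its first value arises during the Week 1 ATTOC visit.
- **Exploratory Aim 2 (Section 7.2.1).** The Dashboard is used to study which ATTOC components matter. Nothing limits it to that use.

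**The concern.** Both measures describe what happened because a clinic was randomised to ATTOC. Adjusting the arm comparison for them removes the part of the effect that works through implementation. It also opens a path through any unmeasured factor that drives both implementation and outcome. What remains is not the contrast that Section 7.2.1 sets out to test.

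For Aim 1 there is a further problem. The Dashboard records provision of counselling, referrals and pharmacotherapy (4.7) and guideline adherence (6.2.2), while the Aim 1 outcome (4.8.1) is asking, advising, assisting and arranging follow-up. The outcome would be partly adjusted for itself.

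The direction of the error cannot be predicted. Shared content makes Dashboard and adherence rise together. Coaching aimed at clinicians whose adherence is unacceptable (6.2.4) puts more implementation effort where the outcome is poor. A real effect can be hidden, or a null effect declared real. For Aim 3, non-inferiority on mental health could be claimed too often or too seldom.

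It is also unclear whether UC clinics have Dashboard values. Section 7.2 speaks of evaluating these measures across arms. Section 9.2, however, describes entry by ATTOC personnel, and Sections 6.2.3 and 6.2.5 give UC no procedures at Weeks 4, 8, 16, 20, 28 and 32. If UC values do not exist, the adjusted arm effect cannot be estimated.

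**Working it through.** **1. The plan's own figures assume no such covariate.** Inputs from Section 7.1: SD 0.87, 280 personnel in 14 sites (m = 20 per site, 7 sites per arm), 80% power, alpha 0.05.

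SE = 0.87 × √(2[1 + 19 × ICC]/140); detectable difference = (t₀.₉₇₅ + t₀.₈₀) × SE on 12 df.

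At ICC 0.05: SE = 0.87 × √(2 × 1.95/140) = 0.145, and (2.179 + 0.873) × 0.145 = 0.443.

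| ICC | Plan | Recomputed |
|---|---|---|
| 0 | 0.32 | 0.317 |
| 0.05 | 0.44 | 0.443 |
| 0.10 | 0.54 | 0.540 |
| 0.15 | 0.62 | 0.623 |

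The stated power is therefore that of an arm-only comparison.

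**2. Adding the Dashboard, Aim 1.** The documents give no Dashboard distribution, so these inputs are assumptions: a 0–1 clinic score; ATTOC mean 0.6 (SD 0.2); UC either all 0 or mean 0.3 (SD 0.2); 50% of the effect mediated. The true effect is 0.44 at ICC 0.05.

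Clinic-mean error SD = 0.87 × √(0.05 + 0.95/20) = 0.272. Let ρ be the correlation between a clinic's Dashboard deviation and its outcome error, and Δ the arm difference in mean Dashboard score (0.6 or 0.3). The adjusted arm coefficient is then

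(1 − 0.5) × 0.44 − Δ × ρ × 0.272/0.2.

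| ρ | UC all 0 (Δ = 0.6) | UC mean 0.3 (Δ = 0.3) |
|---|---|---|
| −0.5 | 0.63 | 0.42 |
| −0.3 | 0.46 | 0.34 |
| 0 | 0.22 | 0.22 |
| +0.3 | −0.02 | 0.10 |
| +0.5 | −0.19 | 0.02 |

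The estimate without the Dashboard is 0.44 throughout. Simulation of clinic means (40,000 runs per scenario; t on 12 df without the Dashboard, 11 df with it) gives the same estimates. At ρ = 0 it gives:

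- UC all 0: power 78% without the Dashboard, 9% with it.
- UC mean 0.3: power 69% without, 19% with.

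**3. No true effect.** Two-sided type I error is 5% without the Dashboard. With it, the error is 9–10% at ρ = ±0.3 and 18–21% at ρ = ±0.5.

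**4. Aim 3.** From Section 7.1: BASIS-R SD 0.8, and 50 clients per site less 15% (m = 42.5). The difference of 0.50 at ICC 0.15 is taken here as the margin, which is an assumption. The test is one-sided at 0.025, with a true worsening equal to the margin and half of it mediated. False non-inferiority is 2.5% without the Dashboard. With it and ρ = 0, it is 7–8% (UC all 0) or 16–17% (UC mean 0.3). Over ρ from −0.3 to +0.3 and both UC assumptions, the range is 2% to 38%.

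**5. Precision and sensitivity.** With no mediation and ρ = 0, the SE of the arm term is multiplied by about 2.6 (UC all 0) or 1.3 (UC mean 0.3). Other Aim 1 inputs (ATTOC mean 0.5 or 0.8, SD 0.1 or 0.3; UC all 0, or mean 0.3 with SD 0.1 or 0.2) give:

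- an adjusted estimate of 0.21–0.23 at 50% mediation and ρ = 0;
- type I error of 7–16% at ρ = ±0.3;
- SE ratios from 0.8 to 6.5, so precision usually falls but not always.

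Centring the Dashboard within arm keeps the estimate at 0.44. The plan specifies no coding.

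**The case against.** The strongest reply is that this is a permission and not a plan. Section 7.2.1 tests an arm term and never names the Dashboard. The Study Summary and Section 7.2 only allow inclusion, and fidelity is only a possible covariate. The one categorical sentence sits in a description of measures, near a dose-type purpose, and the study aims include Exploratory Aim 2, where the Dashboard belongs. All of that is true. But the sentence in 4.7 excepts no aim, the other two places name primary analyses, and nothing excludes the measure. Leaving the choice of primary model open until data are in hand is itself a defect.

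Other points stand in part:

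- Listing the Dashboard under two headings in the schedule proves little, since S-KAP also appears under several. The Covariates list in 4.7 omits the Dashboard, but it omits demographics too. No weight is placed on either.
- The Week 1 value is partly a picture of the clinic before change. It is still taken after randomisation and described only for ATTOC clinics.
- If UC has no Dashboard values, the between-arm model cannot be fitted and the bias figures do not arise. The documents do not settle this.
- The sizes rest on assumed inputs. In the UC 0.3 scenario, Dashboard variation is added to the ICC of 0.05, so the effective ICC is about 0.076 and arm-only power is 69%. For Aim 3, arm-only power at the assumed margin with no true difference is 74%, not the 80% stated in 7.1. Neither affects the comparison with and without the Dashboard.

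**Conclusion.** The point holds and must be fixed. Applied as written, Section 4.7 would condition the primary arm term on a consequence of randomisation that overlaps the Aim 1 outcome. Section 7.2 and the Study Summary permit the same. That conclusion needs no assumed numbers: with the Dashboard entered uncentred, the coefficient is no longer the randomised contrast.

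The size does depend on assumptions about Dashboard scores, the mediated share and shared unmeasured causes. Under those used here, the Aim 1 effect is halved when there is no shared cause and can be raised or reversed when there is one. Type I error can reach about 20%, and false non-inferiority for Aim 3 can reach 38%. The harm arises only if the option is used and UC values exist or are set to a floor. If UC values are absent, the adjusted comparison cannot be made at all.

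**What to change.** 1. **Section 4.7:** replace the statement that the Dashboard serves as a covariate for the study aims with use in Exploratory Aim 2 or a within-ATTOC dose analysis only. Limit the fidelity measure in the same way.
2. **Schedule:** remove the Dashboard row under covariates. It is already listed under treatment data for the same weeks.
3. **Section 7.2 and Study Summary:** delete the clause allowing fidelity and adherence measures into primary analyses.
4. **Section 7.2:** add: *Any covariate in the primary models for Aims 1–3 is a site matching factor (Section 4.2) or a value measured at baseline, before the intervention or training starts. The Dashboard and fidelity measures are not entered in these models.*

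The cost is wording in three places and one schedule row. Data collection does not change. Exploratory Aim 2 keeps its planned use of the Dashboard, and Exploratory Aim 1 is unaffected because it uses the S-KAP and S-KAS barriers. A between-arm model with the Dashboard is given up; if the team wants one, it should be named in advance as exploratory. The matching factors are permitted, not required; entering both would use 2 of the 12 degrees of freedom.
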